
independent samples, or if applicable, with U Mann Whitney, considering $p < 0.05$ as statistical significance and using GraphPad Prism software version 5.

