8. METHODOLOGY

8.1 Study Type: Explanatory

8.2 Design: Double-blind, randomized controlled clinical trial.

8.3 Study population: Adult subjects aged 40-60 years diagnosed with type 2 diabetes mellitus and diabetic neuropathy who attend, by open call, to Anáhuac México Norte University, the Kidney Specialty Center in the State of Mexico, and the Nueva Oxtotitlán clinic (Toluca).

8.4 Sample Size Calculation:

$$N = \frac{2(Z\alpha+Z\beta^2)s^2}{d^2} = N = \frac{2(1.96+0.84^2)(0.84)^2}{(0.776)^2} = N = \frac{(15.68)(0.7056)}{(0.6021)}$$

A total of 18 subjects per group were obtained, considering the following data:

s= Baseline standard deviation: 0.84 (obtained from a study in which probucol and methylcobalamin are used in subjects with DN and the TCSS is used to assess the effect of the intervention.) (49)

d= Proposed difference: 0.776 (refers to the expected difference → 7.5% decrease with respect to the control group)

Z α = 1.96 (value in tables, corresponding to a significance level of 95% for two tails)

Z β = 0.84 (value in tables, corresponding to a power of 80%)

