8.5 Selection criteria

Inclusion Criteria	Non-inclusion Criteria

 - Adults aged 40-60 years with a diagnosis of type 2 diabetes mellitus (T2D) and diabetic neuropathy - Minimum duration of T2DM diagnosis: 5 years. - MNSI (Michigan Neuropathy Screening Instrument) score ≥ 2. - Both genders. - Must sign the informed consent form 	
 - Subjects with known sensitivity or hyperreactivity to cocoa or any of its components. - Pregnant women. - Subjects with neurological diseases, such as multiple sclerosis, epilepsy, or previous cerebrovascular events. - Subjects with implanted electronic devices, e.g., pacemakers. - Subjects with peripheral nerve damage in the lower extremities caused by trauma.

	
 - Subjects with a diagnosis of disc herniation below T10. - History/diagnosis of herpes zoster. - Serological diagnosis of rheumatoid arthritis or systemic lupus erythematosus. HIV/AIDS. - Venous insufficiency (C2-C6 class, asymptomatic/symptomatic according to Nicolaides CEAP classification) in lower limbs. - Clinical hypothyroidism. - Use of orthopedic equipment (e.g., prosthetics, splints, wheelchair, crutches). - Cancer diagnosis, use of oncological drugs and/or radiotherapy, or history of cancer or tumors treated with oncological drugs or radiotherapy. - Smoking, considered positive in those with a smoking index greater than 10. - History of diabetic foot (Wagner Scale 3-5) or amputation. - Presence of ulcers and open and/or extensive wounds (>2 cm) - Allodynia - Sciatic nerve root compression - Gout/Hyperuricemia
--	---

Elimination Criteria

- Subjects who modify their pharmacological treatment during the study.
- Subjects who do not attend one of the intermediate consultations
- Subjects who withdraw informed consent or decide not to continue participating in the

study

- Subjects with less than 80% adherence to cocoa supplementation
- Subjects who miss more than one consultation or do not attend the final consultation.

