Patients will be asked to attend the appointments on an empty stomach, after having urinated and defecated. Weight will be determined according to the Lohman technique, that is, without shoes and with as few clothes as possible, the individual will be placed in the center of the scale and must remain still during the measurement. (54) Waist circumference will be measured according to the proposal of the Ministry of Health of Mexico: placing the tape in a horizontal plane around the waist, taking as reference the mid-axillary line, locating the midpoint between the lower costal margin and the highest lateral edge of the iliac crest (55) and the abdominal circumference: the upper part of the hip bone and the upper part of the right iliac crest are located and the measuring tape is placed in a horizontal plane around the abdomen, at the level of the iliac crest, at the end of a normal expiration. (55) Likewise, blood pressure will be measured using a sphygmomanometer (Nebucor brand, model HL-888JA), according to the Clinical Practice Guide for the Diagnosis and Treatment of Arterial Hypertension in the first level of care (57). These evaluations will be carried out every month, until completing the three months of the duration of the study. In addition, at the beginning of the study the MNSI (Annex 3) will be applied as part of the diagnosis of DN, and both at the beginning and at the end, the TCSS (Annex 4), the questionnaire as the physical examination (51), the BEST questionnaire (Annex 5), the Bristol scale (Annex 6) and the Diabetes 39 quality of life questionnaire (Annex 7) will be applied and laboratory studies will be taken to know the biochemical parameters (triglyceridemia, HDL-c, LDL-c, glycemia,

HbA1c, TG / HDL index and neutrophil/lymphocyte ratio will be determined, as described in the table of variables.

Participants in both groups, being subjects with a cardiometabolic disease, will be nutritionally assisted, that is, all patients will be given a meal plan according to the characteristics of each one of them, calculated by the Mifflin-St. Jeor energy expenditure prediction formula (67) for subjects with obesity, while, according to the Joslin Diabetes Center, a distribution of 40-45% carbohydrates, 30-40% lipids, and 20-30% protein is suggested. (68) Two capsules will be prescribed – cocoa for the experimental group or methylcellulose for the control group – in the morning and two capsules at night.

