pulse should not cause a painful sensation, but it may cause a tingling sensation. The test will be suspended if the individual reports pain or does not wish to continue with the research protocol. For the recording of the H reflex, the active electrode will be placed between the lateral malleolus and the Achilles tendon. Next, the reference electrode will be marked below it and 14 cm will be measured from the active electrode towards the middle of the calf. The "H" reflex test will be performed in two parts. The first part of the protocol consists of determining the curve of stimulus intensity vs. amplitude of the motor responses from the appearance of the "M" wave and the "H" wave, for which the electric current will be increased in steps of 0.5 μ A until the appearance of the waves. For this part, only one electric pulse (1 ms duration) will be given every 10 seconds. The intensity of the electric current that will be used for the second part of the protocol will be that whose value on the curve of amplitude of the H wave-electric current intensity reaches 60% of the maximum amplitude. This stimulation value guarantees the reproducibility and minimum variability of this wave, which also avoids muscle contraction that contaminates the electrical recording. The second part is the paired electrical stimulation test in which two electrical pulses (1 ms duration) will be produced at different frequencies between the pulses: 0.1, 1, 5 and 10 Hz. The interval between the paired pulses will be 10 s, until completing 10 series.

Electrophysiological recordings will be analyzed with Clampfit 10.0 software. The latency and amplitude of the H1 and H2 evoked potentials will be determined for each electrical pulse and at all stimulation frequencies, taking the stimulus artifact as a reference. The ratio of the amplitude of the paired H2/H1 pulses will then be determined to establish the modulation of spinal excitability. A ratio ≥ 0.6 for any stimulation frequency will be considered as an indicator of dysfunction in somatosensory processing according to Marshall et al. (18)

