8.8 STATISTICAL ANALYSIS

A descriptive analysis of all dependent variables, as well as demographic variables, will be performed, expressing them as mean \pm standard deviation or, where appropriate, as median and range (min-max), according to the normality of the data; nominal variables will be expressed as frequencies. Subsequently, an intragroup inferential analysis will be carried out for weight, waist circumference, abdominal circumference and blood pressure with ANOVA for repeated samples with Tukey *post hoc*, and in case the data distribution does not meet the normality criteria, the corresponding nonparametric test will be performed (e.g.,

Friedman, followed by Dunn's *post hoc*). For biochemical analysis (glycemic and lipid profile and markers of inflammation), as well as the evaluations corresponding to diabetic peripheral and autonomic neuropathy, and quality of life, a Student's T test will be performed for dependent groups, or where appropriate, with Wilcoxon.

The intergroup comparison will be made with Student's T test for independent samples, or if applicable, with Mann-Whitney U at each measurement time. A $p < 0.05$ will be considered as statistical significance. All of the above will be carried out using version 5 of the GraphPad Prism software.

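### The between-arm tests ignore baseline values that the trial collects; adjusting for them gains useful precision if baseline and month-3 values correlate at about 0.4 or more

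*Combined protocol and SAP*

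**What the plan says.** Section 8.8 of the combined protocol and SAP gives one between-arm analysis: Student's t-test "for independent samples, or if applicable, with Mann-Whitney U at each measurement time". The Summary names the same pair of tests ("independent samples, or if applicable, with U Mann Whitney"). Neither place mentions ANCOVA, a comparison of change scores, a mixed model or any other comparison of arms that uses baseline.

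Apart from a between-arm test at the baseline visit itself, baseline enters inference only within each arm. For laboratory, neuropathy and quality-of-life outcomes a "T test will be performed for dependent groups", with Wilcoxon as the alternative. For weight, circumferences and blood pressure there is a repeated-measures ANOVA or Friedman test.

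The baseline values exist. Section 8.7 applies, "both at the beginning and at the end, the TCSS (Annex 4"), together with the BEST, Bristol and Diabetes 39 instruments and the laboratory tests. For anthropometry and blood pressure it says "These evaluations will be carried out every month, until completing the three months of the duration of the study". The MNSI is scheduled at the start only. The H-reflex is not in the Section 8.7 list of baseline and final assessments, although the paired test in Section 8.8 implies two recordings.

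**The concern.** Both arms receive a meal plan as well as capsules, so change within an arm mixes diet, time and capsule. Only the comparison between arms isolates cocoa, and that comparison leaves out each patient's starting value. When the same patients are scored twice on the same scale, some positive correlation is a reasonable expectation, and adjusting for baseline then removes variance that the planned test leaves in.

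Two things are at stake. The trial may have a lower chance of detecting its planned TCSS effect than its own data allow. It also cannot correct a chance baseline difference once one has occurred. With 18 per arm, several sites, a random number table and no stated stratification or blocking, such a difference is realistic.

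Testing at every measurement time also implies significance tests at baseline. Among all randomised patients these can reflect only chance.

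**Working it through.** **Inputs.** From Section 8.4: difference d = 0.776 TCSS points; "s= Baseline standard deviation: 0.84", taken from an outside study; two-sided 5% level; 80% power; 18 per group. Assumed: the same SD at month 3, normal data, and a baseline-to-month-3 correlation r from 0 to 0.7.

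**The plan's own figure.** 2(1.96 + 0.84)² × 0.84² / 0.776² = 15.68 × 0.7056 / 0.6021 = 18.4, which rounds up to 19; the plan states 18. (The printed formula squares only Zβ, but its 15.68 shows that the sum was squared.) With 18 per arm, power is 79.1% by the normal approximation and 76.8% by the t distribution.

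**Formulas, n per arm.**
- Unadjusted t-test: SE = 0.84 × √(2/n), with 2n − 2 degrees of freedom. At n = 18, SE = 0.280.
- ANCOVA: SE = 0.84 × √(2/n) × √[(1 − r²)(1 + 1/(2n − 4))], with 2n − 3 degrees of freedom. The last factor is the expected cost of estimating the baseline slope; at n = 18 it is 1 + 1/32 = 1.031.
- Power for d comes from the noncentral t distribution.

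**Results at 18 per arm.**

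| Analysis | Variance ratio to t-test | SE | Power | 95% CI half-width |
|---|---|---|---|---|
| Unadjusted | 1 | 0.280 | 76.8% | 0.57 |
| ANCOVA, r = 0 | 1.03 | 0.284 | 75.5% | 0.58 |
| r = 0.2 | 0.99 | 0.279 | 77.1% | 0.57 |
| r = 0.3 | 0.94 | 0.271 | 79.3% | 0.55 |
| r = 0.4 | 0.87 | 0.261 | 82.4% | 0.53 |
| r = 0.5 | 0.77 | 0.246 | 86.4% | 0.50 |
| r = 0.7 | 0.53 | 0.203 | 96.0% | 0.41 |

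Simulation of bivariate normal data agrees; at r = 0.5 it gave 77.0% for the t-test and 86.5% for ANCOVA. For scale, ANCOVA at r = 0.5 with 18 per arm has about the power of the unadjusted test with 23 per arm (86.5%).

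**Break-even.** On variance, (1 − r²) × 1.031 = 1 gives r = 0.17. On power it is 0.18.

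**Fewer analysed.** Section 8.5 eliminates, among others, "Subjects with less than 80% adherence to cocoa supplementation". How many will go is unknown, so 14 and 10 per arm are assumed examples.
- 14 per arm: 65.3% unadjusted, against 63.4, 67.5 and 75.7% with ANCOVA at r = 0, 0.3 and 0.5. Break-even is 0.21.
- 10 per arm: 49.8%, against 47.2, 50.9 and 58.8%. Break-even is 0.255.

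**Larger SD (assumed), 18 per arm, r = 0.5.** SD 1.5: 32.6% unadjusted against 40.3% with ANCOVA. SD 2.0: 20.5% against 25.0%.

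**Source of the cost at r = 0.** At 18 per arm the lost degree of freedom alone moves power from 76.81% to 76.73%; the rest of the fall to 75.5% comes from estimating the slope.

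**Chance imbalance, no true effect, 18 per arm (100,000 simulated trials per r).** The baseline difference is at least 0.28 (one standard error, an illustrative cut-off) in about 32% of randomisations. In those, the planned test is positive in 6.5, 8.9 and 12.1% at r = 0.3, 0.5 and 0.7. In the others it is positive in 4.4, 3.2 and 1.6%. Overall it is 5.0%. ANCOVA stays near 5% in both groups.

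**The case against.** The strongest reply is that this concerns efficiency, not error. A reader might infer that the planned comparison is invalid or biased. The documents do not support that: with all randomised patients analysed, the type I error is 5% over repeated randomisations. The conditional error rates average to that 5%, depend on a chosen cut-off and apply to any unadjusted test, so they illustrate the point and do not show a fault peculiar to this plan.

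The gain also rests on a correlation that the documents do not give. At r = 0.2 it is 0.3 points of power, and at 0.3 it is 2.5 points. A reader who takes the break-even value as the point where adjustment starts to matter would overstate the case. The SD is a baseline figure from another study; if the true SD is larger, absolute power falls and neither analysis is adequate, although the variance ratio is unchanged. The power figures also compare ANCOVA with the t-test, not with Mann-Whitney.

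A third tempting reading is that ANCOVA makes good the removal of patients. It does not. If the tests use only those left after the Section 8.5 eliminations, baseline differences may reflect selection as well as chance, the 5% is no longer guaranteed for either test, and adjustment within that subset does not restore randomisation.

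Finally, Section 10 schedules the statistical analysis for January to June 2022, and the document was last updated in March 2025. The analysis may be done; the documents do not say.

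All of this stands as a limit on the point. None of it removes the omission.

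**Conclusion.** The point holds as a recommended improvement. The plan has no baseline-adjusted comparison of arms, although it collects the baseline values needed for most outcomes. That the adjustment is absent is certain; the size of the benefit is not.

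Under the stated assumptions the trade is lopsided. At 18 per arm ANCOVA loses about 1 point of power if r is near 0, and gains 5.6 points at r = 0.4 (82.4 − 76.8), 9.6 at 0.5 and 19.2 at 0.7. Materially useful gains start at about r = 0.4. The 5% error rate, and the statement that baseline differences are due to chance, both depend on analysing all randomised patients.

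**What to change.** In Section 8.8:

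- Make the month-3 between-arm analysis an ANCOVA of the month-3 value on arm plus the baseline value of the same variable. Report the adjusted difference and its 95% CI.
- Apply it to TCSS total score, BEST, Diabetes 39, laboratory values and ratios, weight, circumferences, waist-to-height ratio and blood pressure. For outcomes measured monthly, use the same baseline-adjusted model at months 1 and 2.
- Name skewed outcomes in advance. For these use a log scale, with an adjusted ratio and CI, or a rank ANCOVA for the p-value with an unranked estimate beside it, since ranks give no difference in original units.
- Include the H2/H1 ratio only if a baseline recording is made, and then separately at each setting ("different frequencies between the pulses: 0.1, 1, 5 and 10 Hz"). State the timing of the recordings.
- Leave out the MNSI, which is measured at baseline only, and Bristol type, where both ends of the scale are abnormal and improvement must be defined first.
- Drop significance tests at baseline.

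Fix this before unblinding. If the data have already been analysed, report the ANCOVA as post hoc beside the planned test.

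The cost is SAP wording and software that fits the model; whether the named GraphPad Prism version can do so should be checked. Outcomes with a baseline value need no new data. If r is near 0, the price is about 1 point of power at 18 per arm and about 2.6 points at 10 per arm (49.8% to 47.2%), mostly from estimating the baseline slope.

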9. ETHICAL CONSIDERATIONS

This study complies with the guidelines stipulated in the International Ethical Guidelines for Biomedical Research Involving Human Subjects, in the Declaration of Helsinki (69) and the Nuremberg Code (70), as well as the NOM-012-SSA3-2012. (71) In terms of national regulation, it adheres to the Regulations of the General Health Law on Research, within whose article 17, this protocol is considered research with greater than minimum risk due to the random method of assignment to the intervention scheme. (72) Considering the level of risk, and in accordance with the provisions of article 14, informed consent must be in writing, so each subject who participates in the study, as detailed in the Methodology section, will be informed and explained the procedures to be carried out in order to subsequently record in writing their decision to participate in an informed consent letter, in accordance with Chapter I of the General Health Law regarding the ethical aspects of research in human beings (Annex 1).

Likewise, the protocol will be submitted to the research and Bioethics committees of the Faculty of Health Sciences of the Universidad Anáhuac México Norte.

A nutrition plan will be given for the prevention or correction of obesity and to contribute to metabolic control, as indicated by the Mexican Official Standard 015-SSA2-2010 for the Prevention, Treatment and Control of Diabetes Mellitus. (76)

10. SCHEDULE OF ACTIVITIES

ACTIVITY	August-December 2020	January – December 2021	January – June 2022	July – December 2022	January – June 2023
Submission, evaluation, correction Health Science Faculty Committee protocol	X	X			
Patient recruitment and experimental development		X			
Information coding and emptying in the database		X	X		
Statistical analysis			X		
Preparation of final report				X	
Publication of Results and obtaining a degree					X

Appendix 2: Cocoa capsules

ATENCIÓN:
NO CONSUMIR DURANTE EL EMBARAZO NI POR MENORES DE 10 AÑOS.
Modo de empleo: Tomar 2 cápsulas antes de cada alimento.
No exceda la dosis recomendada. Manténgase en un lugar
fresco y seco. Fuera del alcance de los niños.

SUPLEMENTO ALIMENTICIO con polifenoles de cacao

ESTE PRODUCTO NO ES UN MEDICAMENTO.
Su uso es responsabilidad
de quien lo usa y lo recomienda

Frasco con 60 cápsulas

SUPLEMENTO ALIMENTICIO a base de cacao

Contenido neto: 60 cápsulas de 500mg.

Ingredientes: Cacao en polvo (Theobroma cacao)

INFORMACIÓN NUTRIMENTAL

Tamaño de la porción: 2 cápsulas (1g)

Porciones por envase: 30

	Por 100g	Por porción
Contenido energético kJ (Kcal)	109 (257)	1.09 (2.57)
Proteínas (g)	6.0	0.06
Grasas (lipidos) de las cuales (g):	1.0	0.01
Grasas saturadas (g)	0.15	0.85
Grasas insaturadas (g)	0.85	0.15
Carbohidratos (g) (hidratos de carbono)	56	0.56
Fibra dietética (g)	25g	0.25g
Sodio (mg)	11.54	0.11

Hecho en México por
Cacao & Health

Lote: 001-17

Fecha de caducidad: 08/2018

Hecho en México por Tecnología en Ciencia y Salud. Promotores de
desarrollo. [name],
Baja California, México.

Appendix 3 “*The Michigan Neuropathy Screening Instrument*” (MNSI) Instrument

1. Are your legs and/or feet numb?	 No	 Yes
2. Do you ever have any burning pain in your legs and/or feet?	 No	 Yes
3. Are your feet too sensitive to touch?	 No	 Yes
4. Do you get muscle cramps in your legs and/or feet?	 No	 Yes
5. Do you ever have any prickling feelings in your legs or feet?	 No	 Yes
6. Does it hurt when the bed covers touch your skin?	 No	 Yes
7. When you get into the tub or shower, are you able to tell the hot water from the cold water?	 No	 Yes
8. Have you ever had an open sore on your foot?	 No	 Yes
9. Has your doctor ever told you that you have diabetic neuropathy?	 No	 Yes
10. Do you feel weak all over most of the time?	 No	 Yes
11. Are your symptoms worse at night?	 No	 Yes
12. Do your legs hurt when you walk?	 No	 Yes
13. Are you able to sense your feet when you walk?	 No	 Yes
14. Is the skin on your feet so dry that it cracks open?	 No	 Yes
15. Have you ever had an amputation?	 No	 Yes

Total: _____

Appendix 4: Toronto Clinical Scoring System (TCSS)

Symptom scores	Reflex scores	Sensory test scores
Foot	Knee reflexes	Pinprick
Pain	Ankle reflexes	Temperature
Numbness		Light touch
Tingling		Vibration
Weakness		Position
Ataxia		
Upper-limb symptoms		

Sensory testing was performed on the first toe. Symptom scores: present = 1; absent = 0. Reflex scores: absent = 2; reduced = 1, normal = 0. Sensory test score: abnormal = 1, normal = 0. Total scores range from normal = 0 to maximum of 19.

Appendix 5: BEST questionnaire

TABLA 2. Cuestionario BEST para evaluar el impacto de los síntomas de un intestino irritable sobre la CVRS

1. Durante las últimas 4 semanas, ¿Cómo se ha sentido en relación a su hábito de defecar?
 - Muy bien: mis deposiciones han sido normales.
 - Bien: apenas ha habido alteraciones en mi ritmo intestinal y, de hecho, las he ignorado.
 - Regular: no he podido ignorar las alteraciones en mi ritmo intestinal.
 - Mal: las alteraciones de mi ritmo intestinal han llegado a afectar a mi estilo de vida.
 - Muy mal: las alteraciones del ritmo intestinal han afectado gravemente a mi estilo de vida.
2. Lea Vd. la siguiente declaración y diga lo que opina sobre ella: "Los síntomas intestinales que estoy sufriendo significan que algo muy serio está ocurriendo en mi cuerpo".
 - No, de ninguna manera.
 - Sí, quizás en algún momento, pero muy pocas veces.
 - Sí, algo sí.
 - Sí, bastante.
 - Sí, mucho.
3. Durante las últimas 4 semanas, ¿con qué frecuencia sus síntomas intestinales han hecho que se sienta tenso o profundamente afectado?
 - La mayoría del tiempo.
 - En muchas ocasiones.
 - Solo muy de vez en cuando.
 - En ningún momento.
4. Díganos lo que piensa sobre la siguiente frase: "Debido a los síntomas intestinales que sufro, durante las últimas 4 semanas no he podido disfrutar de las cosas que antes me divertían".
 - De ninguna manera me ha ocurrido esto.
 - Sí, quizás en algún momento, pero muy pocas veces.
 - Sí, algo sí.
 - Sí, bastante.
 - Sí, mucho.

Las respuestas a estas preguntas se miden en una escala de 0 (el mejor estado de salud) a 100 (el peor estado de salud). La calificación final asignada de acuerdo a un algoritmo estándar se entrega al médico, antes de que éste entre en la consulta. [Spiegel BMR, Naliboff, Mayer E, et al. Development and initial validation of a concise point-of-care IBS severity index: the 4-item BEST questionnaire. *Gastroenterology* 2006;130:S1040].

